13.6 Stipends for Participation

Expenses that are directly related to the subject's participation in the trial (for example cost of transportation for attending visits) will be reimbursed. Subjects/subjects' parent(s)/legally acceptable representative(s) will not receive any remuneration for participation in the trial.

This trial (CYD65) is a two-stage Phase II trial of Sanofi Pasteur's CYD dengue vaccine that will assess the immunogenicity and safety of CYD dengue vaccine in healthy adolescents and adults who will receive 3 primary doses of tetravalent CYD dengue vaccine (each dose administered 6 months apart) (STAGE I) and a booster dose of the same vaccine either 1 or 2 years following the last dose in the primary series (STAGE II). The CYD65 study is conducted in two endemic countries, one in Latin America (Colombia) and one in Asia (the Philippines) and includes subjects from 9 to 50 years of age. This age group was chosen based on the long-term follow-up from previous studies, where it was observed that not all subjects below 9 years of age benefitted from CYD dengue vaccine.

Dengue disease is caused by 4 closely related, but antigenically distinct, dengue virus serotypes (1, 2, 3, and 4) of the genus flavivirus (FV). Infection with a dengue virus is usually asymptomatic but can produce a spectrum of clinical illnesses ranging from a non-specific viral syndrome to severe, fatal hemorrhagic disease.

Dengue fever (DF) is characterized by biphasic fever, headache, pain in various parts of the body, prostration, rash, and lymphadenopathy. Recovery from DF is usually complete in 7 to 10 days, but prolonged asthenia is common. Decreases in leukocytes and platelet count are frequent. The incubation period of DF after the mosquito bite averages 4 days (range from 3 to 14 days).

At present, no specific treatment exists for dengue disease. As of March 2019, the CYD dengue vaccine (commercial name Dengvaxia®) has been registered in 20 of : Argentina, Australia, Bangladesh, Bolivia, Brazil, Cambodia, Costa Rica, Dominican Republic, El Salvador, Europe, Guatemala, Honduras, Indonesia, Myanmar, Mexico, Paraguay, Peru, Singapore, Thailand, and Venezuela. Other than vaccination, preventive measures rely on mosquito control and personal protection. However, these measures are limited in efficacy, difficult to enforce, and expensive. The best method of prevention lies with the development of a safe and effective vaccine directed at the 4 serotypes of dengue virus responsible for the disease.

This statistical analysis plan (SAP) includes detailed procedures for executing statistical analysis of the primary and secondary variables and other data. Its purposes are the following:

- To state the objectives of this study
- To clearly define all variables (raw and derived), criteria and parameters that will be used for statistical analyses
- To describe statistical methods that will be used for analyses; descriptive statistics used are listed
- To define populations used for analyses

2 Trial Objectives

2.1 Primary Objectives

STAGE I:

- To demonstrate the non-inferiority (NI) of the immune response elicited against each dengue serotype by the CYD dengue vaccine given as a 2-dose schedule (Group 2) compared to the immune response elicited by CYD dengue vaccine given as a 3-dose schedule (Group 1), in subjects seropositive at baseline, 28 days after last injection, in terms of Geometric Mean Ratio (GMR).
- To demonstrate the NI of the immune response elicited against each dengue serotype by the CYD dengue vaccine given as a 2-dose schedule (Group 2) compared to the immune response elicited by CYD dengue vaccine given as a 3-dose schedule (Group 1), in subjects seropositive at baseline, 1 year after last injection, in terms of GMR.

STAGE II:

- To demonstrate the NI of the immune response elicited against each dengue serotype, in subjects seropositive at baseline, 28 days after administration of a booster dose of CYD dengue vaccine in terms of geometric mean of titer ratio (GMTR, within a group) or GMR (between groups):

Booster Dose at One Year

- Post-Year 1 booster Group 1/post-Dose-3 Group 1 (GMTR)
- Post-Year 1 booster Group 2/post-Dose 3 Group 1 (GMR)*

Booster Dose at Two Years

- Post-Year 2 booster Group 1/post-Dose 3 Group 1 (GMTR)
- Post-Year 2 booster Group 2/post-Dose 3 Group 1 (GMR)*

* *Note: The STAGE II Primary Objectives involving Group 2 will apply only if NI has been achieved in STAGE I; within Group 1 testing in STAGE II will be performed regardless of the STAGE I test results*

2.2 Secondary Objectives

Immunogenicity

STAGE I:

- To demonstrate the superiority of the immune response elicited by CYD dengue vaccine given as a 2-dose schedule (Group 2) compared to the immune response elicited by CYD dengue vaccine given as a 3-dose schedule (Group 1), in subjects seropositive at baseline, 28 days after last injection, in terms of GMR.

- To demonstrate the superiority of the immune response elicited by CYD dengue vaccine given as a 2-dose schedule (Group 2) compared to the immune response elicited by CYD dengue vaccine given as a 3-dose schedule (Group 1), in seropositive subjects at baseline, 1 year after last injection, in terms of GMR.

Note: NI has to be achieved before assessing for superiority

- To describe the neutralizing Ab levels of each dengue serotype at 28 days post-Injection 3 to the Ab levels immediately before receiving booster injection by baseline serostatus in all 3 groups.
- To describe the neutralizing Ab levels of each dengue serotype at 28 days post-Injection 2 and 28 days post-Injection 3 from Group 1 in a primary series schedule by baseline serostatus.

STAGE II:

- To demonstrate the superiority of the immune response elicited against each dengue serotype, in subjects seropositive at baseline, 28 days after administration of a booster dose of CYD dengue vaccine in terms of GMTR (within group) or GMR (between groups):

Booster Dose at One Year

- Post-Year1 booster Group 1 compared to post-Dose 3 Group 1 (GMTR)
- Post-Year 1 booster Group 2 compared to post-Dose 3 Group 1 (GMR)

Note: NI has to be achieved before assessing for superiority

Booster Dose at Two Years

- Post-Year 2 booster Group 1 compared to post-Dose 3 Group 1 (GMTR)
- Post-Year 2 booster Group 2 compared to post-Dose 3 Group 1 (GMR)

Note: NI has to be achieved before assessing for superiority

- To describe the seroconversion rate 28 days after booster injection in all 3 groups.

Safety

STAGE I and STAGE II

- To describe all hospitalized virologically-confirmed dengue (VCD) cases that have occurred at any time during the trial
- To evaluate the safety profile of CYD dengue vaccine after each and any injection (reactogenicity; unsolicited adverse events (AEs); serious adverse events (SAEs) throughout the trial and for 6-months following end of trial; and adverse events of special interest (AESIs) at defined time windows throughout the trial according to the type of AESI)

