2.2 Secondary Objectives

Immunogenicity

STAGE I:

- To demonstrate the superiority of the immune response elicited by the CYD dengue vaccine given as a 2-dose schedule (Group 2) compared to the immune response elicited by CYD dengue vaccine given as a 3-dose schedule (Group 1), in subjects seropositive at baseline, 28 days post-final injection, in terms of GMR.

- To demonstrate the superiority of the immune response elicited by the CYD dengue vaccine given as a 2-dose schedule (Group 2) compared to the immune response elicited by CYD dengue vaccine given as a 3-dose schedule (Group 1), in subjects seropositive at baseline, 1 year post-final injection, in terms of GMR

Note: NI has to be achieved before assessing for superiority

- To describe the neutralizing Ab levels of each dengue serotype at 28 days post-Injection 3 to the Ab levels immediately before receiving booster injection, by baseline serostatus, in all 3 groups.
- To describe the neutralizing Ab levels of each dengue serotype at 28 days post-Injection 2 and 28 days post-Injection 3 from Group 1 in a primary series schedule, by baseline serostatus.

STAGE II:

- To demonstrate the superiority of the immune response elicited against each dengue serotype, in subjects seropositive at baseline, 28 days after administration of a booster dose of CYD dengue vaccine in terms of GMTR (within group) or GMR (between groups):

Booster Dose at One Year

- Post-Year1 booster Group 1 compared to post-Dose 3 Group 1 (GMTR)
- Post-Year 1 booster Group 2 compared to post-Dose 3 Group 1 (GMR)

Note: NI has to be achieved before assessing for superiority

Booster Dose at Two Years

- Post-Year 2 booster Group 1 compared to post-Dose 3 Group 1 (GMTR)
- Post-Year 2 booster Group 2 compared to post-Dose 3 Group 1 (GMR)

Note: NI has to be achieved before assessing for superiority

- To describe the seroconversion rate 28 days after booster injection in all 3 groups.

Safety

STAGE I and STAGE II

- To describe all hospitalized VCD cases that have occurred at any time during the trial
- To evaluate the safety profile of CYD dengue vaccine after each and any injection (reactogenicity; unsolicited AEs; SAEs throughout the trial and for 6-months following any injection; and AESIs at defined time windows throughout the trial according to the type of AESI)

The endpoints for the secondary objectives are presented in Section 9.2.1.1 and Section 9.2.2.2.

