9.2.2.3.4 Serious Adverse Events

Information on SAEs will be collected and assessed throughout the trial, from inclusion until 6 months after booster injection.

Any SAE occurring at any time during the trial will be reported by the Investigator through the EDC system and according to the completion guidelines provided by the Sponsor. All information concerning the SAE is to be reported, either as part of the initial reporting or during follow-up reporting if relevant information became available later (eg, outcome, medical history, results of investigations, copy of hospitalization reports). The Investigator will assess the causal relationship between the SAE and the investigational product as either “Not related” or “Related”, as described in [Section 10.4](#).

See [Section 10](#) for further details on SAE reporting.

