4.4.2.3 SAEs

4.4.2.3.1 Last Vaccination

Last vaccination before an SAE is derived from the last visit numbers provided in the clinical database and is calculated as follows:

- If an SAE has a non-missing visit number, the visit number should be used to determine the last vaccination before the SAE
- If the visit number is missing, then the start date should be used to determine the last vaccination before the SAE

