4.4.2.3.2 Time of Onset

Time of onset will be computed using the same methodology than for unsolicited non-serious AEs described in [Section 4.4.2.2.4](#).

SAEs will be analyzed throughout the study using the following periods:

- Within 28 days after injection
- During the study (i.e., all SAEs occurred during the study)

An SAE with missing time of onset will be considered to have occurred after the vaccination indicated by the visit number, so will be included in these tables. SAEs collected after Visits 1, 3, 5, 7, 8, or 9 with missing time of onset will be included in the table of SAEs analyzed “within 28 days” after the respective injection.

Note: SAEs that occurred before vaccination (negative time to onset) will not be included in analysis, but will be listed separately.

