5.1.2.2.2 Statistical Methods for Other Objectives

5.1.2.2.2.1 Immunogenicity

STAGE I:

In addition, immunogenicity will be assessed using the following parameters:

- Geometric means of the individual titer ratios (GMTR) for each serotype (parental strains) by baseline serostatus (1 year post-Dose 3 /28 days post-Dose 3)
- Group 1 only, GMTR for each serotype (parental strains) by baseline serostatus (28 days post-Dose 3 /post-Dose 2)

STAGE II:

- Seroconversion rates 28 days after the booster for each serotype (parental strains) of CYD dengue vaccine

5.1.2.2.2.2 Safety

STAGES I AND II:

Safety profile will be described after each injection for primary schedules and for booster dose.

The safety analysis will address the number and percentage of subjects with injection site reactions (pain, erythema, and swelling) from D0 and D07, solicited systemic reactions (fever, headache, malaise, myalgia, and asthenia) from D0 to D14, unsolicited AEs until D28, non-serious AESIs from D0 to D07, and unsolicited immediate systemic event occurring within 30 minutes after each injection. Solicited injection site reactions or solicited systemic reactions will be described according to time of onset, number of days of occurrence, action taken, and intensity.

Unsolicited AEs or non-serious AESIs will be described according to nature (MedDRA preferred term), time to onset, duration, intensity, action taken, and relationship to vaccination.

Unsolicited immediate systemic events will be described according to nature (MedDRA preferred term) and relationship to vaccination.

The number and percentage of subjects with SAEs, including serious AESIs will be described according to nature (MedDRA preferred term), seriousness criteria, outcome, and relationship to vaccination throughout the trial.

All AEs leading to study termination will be described according to nature (MedDRA preferred term) and relationship to vaccination.

Detection of symptomatic dengue cases

The number and percentage of subjects with a hospitalized VCD cases occurring during the trial after the injection will be described using safety analysis set.

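### The SAP moves the six-month SAE window from after each injection to after the end of the trial, without listing the change, and plans no six-month SAE summary per injection

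*SAP*

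**What the plan says.** - **Objective in the protocol.** Section 2.2 sets out to evaluate "SAEs throughout the trial and for 6-months following any injection". The synopsis has the same objective.
- **Objective in the SAP.** Section 2.2 reads "serious adverse events (SAEs) throughout the trial and for 6-months following end of trial".
- **Collection.** Protocol 9.2.2.3.4 states: "Information on SAEs will be collected and assessed throughout the trial, from inclusion until 6 months after booster injection". SAP 3.2 likewise follows safety to six months after each booster, and SAP 5.4 places the end of the study six months after the Year 2 booster.
- **Analysis periods.** SAP 4.4.2.3.2 says "SAEs will be analyzed throughout the study using the following periods" and names two: "Within 28 days after injection", and the whole study.
- **Link to an injection.** SAP 4.4.2.3.1 says "Last vaccination before an SAE is derived from the last visit numbers provided in the clinical database".
- **Per-injection description.** SAP 5.1.2.2.2.2 says "Safety profile will be described after each injection for primary schedules and for booster dose".
- **Treatment labels.** SAP 5.2.3 analyses each dose by the product received at that dose, and the any-dose analysis by the product received at the first dose.
- **List of changes.** SAP 5.7, which sets out departures from Protocol Amendment 1, does not mention the SAE window.

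**The concern.** The two objectives name different windows. The SAP's version starts where scheduled follow-up stops, so it cannot be met as written. Its analysis section does not make good the loss, because neither SAE period is six months after an injection.

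The placebo doses make this matter. Group 2 receives placebo at Injection 1 and Group 3 at Injections 1 and 2; from Injection 3 everyone has received CYD. The intervals after Injections 1 and 2 are therefore the only time with a concurrent randomised placebo arm: 350 CYD against 700 placebo, then 700 against 350. A 28-day cut keeps a small part of that time. Protocol 1.4 describes a risk of severe disease in seronegative vaccinees that appears in the longer term, which a 28-day window is poorly placed to show.

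**Working it through.** **1. The plan's own safety figure.** Protocol 12.5 and SAP 5.5 claim a 95% probability of observing an AE with true incidence above 0.85% in a group of 350. Check: 1 − (1 − 0.0085)^350 = 0.9496. The incidence giving exactly 95% is 1 − 0.05^(1/350) = 0.852%. The claim reproduces. The documents give no corresponding figure for a six-month SAE window.

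**2. Share of the placebo-controlled interval covered by the 28-day period.** Injections are planned at D0, D180 and D365 (SAP 3.2).
- After Injection 1: 28/180 = 15.6%. With the ±20-day visit window, 28/200 = 14.0% to 28/160 = 17.5%.
- After Injection 2 (nominally 185 days): 28/185 = 15.1%.

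**3. Placebo person-time.** This uses planned sizes, no dropout, and 700 subjects on placebo after Injection 1 and 350 after Injection 2.
- 28-day windows: (700 × 28 + 350 × 28)/365.25 = 80.5 person-years.
- 180-day windows: (700 × 180 + 350 × 180)/365.25 = 517.5 person-years.
- CYD time over the two windows is the same by symmetry (350 then 700 subjects): 80.5 and 517.5.

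**4. What the whole-study table holds under the first-dose label.** Groups 2 and 3 carry a placebo label throughout. Group 2 spends 6 months and Group 3 spends 12 months before their first CYD dose. With equal follow-up of T months per subject, the share of placebo-labelled time before any CYD is (6 + 12)/(2T):
- T = 30: 18/60 = 30%.
- T = 42: 18/84 = 21%.

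The range 30 to 42 months is the planned participation in SAP 3.1. So 70% to 79% of the time labelled placebo follows a CYD dose.

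**5. Effect on seeing an event at all.** Six-month SAE incidence is not given in the documents, so it is assumed here, with a constant hazard. The 28-day risk is 1 − (1 − p)^(28/180), and the chance of at least one case among 350 is as follows.

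| Assumed six-month incidence p | Over 180 days | Over 28 days |
|---|---|---|
| 0.5% | 83% | 24% |
| 0.85% | 95% | 37% |
| 1% | 97% | 42% |
| 2% | 99.9% | 67% |

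**The case against.** A reader might infer that the SAP produces no placebo-controlled SAE comparison. The documents do not support that. Safety is described after each injection, in a per-dose set by product received, so 28-day SAEs on CYD and placebo will be tabulated at Injections 1 and 2. The comparison is shortened, not absent.

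A reader might also infer that six-month results are out of reach. They are not. Each SAE is assigned to its last vaccination, and Injections 1 to 3 are about six months apart. Whole-study SAEs split by last injection would therefore approximate six months after Injections 1 and 2. After the booster they would do so too, because scheduled follow-up ends with the six-month call. This stands as a possibility, but the SAP does not say the table will be split that way. It would not work for Injection 3, after which the next dose comes at 12 or 24 months, or never for seronegative subjects.

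The best defence is that the six-month phrase only sets how long SAEs are collected. The protocol's SAE endpoint (9.2.2.2) and analysis text (12.1.2) say throughout the trial, and name no six-month table and no risk difference. That is a fair reading of those sections, and it means the SAP removes no table the protocol had specified. It does not explain why the SAP restated the objective with a window that contradicts its own follow-up. The phrase may well be a drafting slip, and the post-trial period is not wholly empty: Protocol 10.3 requires SAEs likely to be related to be reported after completion. But nothing is scheduled then.

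Two further points stand. Hospitalised virologically-confirmed dengue has its own objective and is described for the whole trial. And the comparison would be imprecise: at an assumed six-month risk of 1%, the 95% half-width for a risk difference is 1.96 × √(0.01 × 0.99 × (1/350 + 1/700)) = 1.28 percentage points, larger than the risk itself.

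**Conclusion.** The point holds as a mismatch in the objective and a gap in planned tabulation. The SAE window in SAP 2.2 differs from the protocol's, does not fit the SAP's own end of study, and is not declared in SAP 5.7. No six-month SAE period per injection is defined. As written, CYD against concurrent placebo is shown for SAEs over about 16% of a 180-day interval, or some 80 of 518 placebo person-years.

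The percentage rests only on the planned injection days; the person-years also assume 350 per group and no dropout. The 21% to 30% figure takes the whole-study table to be an any-dose analysis under SAP 5.2.3. If it were shown by randomised group instead, Groups 2 and 3 would still mix placebo and CYD time. The detection probabilities depend on assumed incidences and a constant hazard, and are illustrative.

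It would be too strong to say that the data are lost or that the protocol requires a formal between-product test. SAEs are collected throughout, safety is analysed descriptively, and the immunogenicity hypotheses are unaffected.

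**What to change.** - Restore the protocol's wording of the SAE objective in SAP 2.2. If the sponsor means to change it, list and justify the change in SAP 5.7.
- Add a third period to SAP 4.4.2.3.2: within six months after injection, ending at the next injection if that comes earlier. Apply it to Injections 1, 2 and 3 and to the booster.
- Tabulate it descriptively by product received at that injection, with the exact 95% CIs the SAP already uses for percentages.
- State whether whole-study SAEs will also be split by last injection, and under which treatment label they are shown.

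A CYD-minus-placebo risk difference for Injections 1 and 2 is optional; the protocol does not ask for it. The cost is a wording correction and one extra set of tables. No new data are needed: SAEs are already collected throughout, with six-month safety calls after Injection 3 and after each booster.

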2.3 Additional Objectives

Immunogenicity

STAGE I:

- To describe the neutralizing Ab response of flavivirus (dengue/Japanese Encephalitis [JE] in the Philippines, and dengue/YF in Colombia) serological status by age group and country at baseline in all 3 groups.
- To describe the neutralizing Ab response to each dengue serotype at each available time point by baseline serostatus in all 3 groups.
- To compare the immune response elicited against each dengue serotype by the CYD dengue vaccine given as a 2-dose schedule (Group 2) or a 1-dose schedule (Group 3) and given as a 3-dose schedule (Group 1) at 28 days after last injection, in subjects seropositive at baseline, in terms of GMR.
- To compare the immune response elicited against each dengue serotype by the CYD dengue vaccine given as a 2-dose schedule (Group 2) or a 1-dose schedule (Group 3) and given as a 3-dose schedule (Group 1) at 1 year after last injection in subjects seropositive at baseline, in terms of GMR.

STAGE II:

Booster Dose at One and Two Years

- To describe the neutralizing Ab response to each dengue serotype 28 days after a booster injection

One Year Booster:

- To describe the immune response elicited against each serotype 28 days after administration of a booster dose of CYD dengue vaccine 1 year after the last primary series vaccination in a 2-dose schedule (Group 2) or 1-dose schedule (Group 3) when compared to a 3-dose schedule (Group 1)

Two Year Booster:

- To describe the immune response elicited against each serotype 28 days after administration of a booster dose of CYD dengue vaccine 2 years after the last primary series vaccination in a 2-dose schedule (Group 2) or 1-dose schedule (Group 3) when compared to a 3-dose schedule (Group 1)

STAGE I and STAGE II Additional Immunological Tests (AIT) Subset Only:

- To describe dengue neutralization Ab levels (exploration of Ab response kinetics), Ab specificity and affinity maturation in a subset of subjects (N=60) in all groups (Ratio between subgroups 1:1 = 10 subjects per subgroup).
- To describe cell-mediated immune (CMI) responses at Day 0 [STAGE I] and at 0, 7, 14, 28 days post-booster dose (Y1 and Y2) in this subset of subjects participating in all groups

Note: It is to be noted that the 1:1 ratio per subgroup and N=60 are unlikely to hold as only subjects dengue seropositive at baseline will be eligible to booster injection.

3 Description of the Overall Trial Design and Plan

